8.2 Potential Risks of **CPX-351**

COMMON, SOME MAY BE SERIOUS	
In 100 people receiving CPX-351 more than 10 and up to 100 may have:	
	
▪ Abdominal pain▪ Anemia▪ Anxiety▪ Arrhythmia▪ Chest pain▪ Chills▪ Constipation▪ Cough▪ Decreased appetite▪ Delirium▪ Diarrhea▪ Dizziness▪ Dyspnea▪ Edema▪ Fatigue▪ Febrile neutropenia▪ Fungal infection▪ Headache▪ Hemorrhage▪ Hypertension▪ Hypotension▪ Hypoxia▪ Rash▪ Mucositis▪ Musculoskeletal pain

- Nausea
- Neutropenia
- Non-conduction cardio toxicity
- Pleural effusion
- Pneumonia
- Pruritus
- Pyrexia
- Rash
- Sleep disorders
- Vomiting

OCCASIONAL, SOME MAY BE SERIOUS

In 100 people receiving CPX-351 from 4 to 20 may have:

- Acute renal failure
- Cellulitis
- Catheter/injection site reaction
- Ejection fraction decreased
- Fatigue
- Hemorrhoids
- Hypokalemia
- Malignant neoplasm progressive
- Petechiae
- Pneumonia
- Pyrexia
- Rash
- Sepsis
- Urinary tract infection
- Renal insufficiency
- Respiratory failure
- Transfusion reactions
- Upper respiratory induction (excluding fungal)
- Visual impairments (except bleeding)

8.3 SAE Report Form

SAEs will be recorded on the FDA Form 3500A (MedWatch) but should only be reported as instructed below. The electronic FDA SAE reporting forms should not be used.

8.4 Reporting Procedures for Serious Adverse Events

For the purposes of safety reporting, all adverse events will be reported that occur through 30 days after the final dose of study drug. Adverse events, both serious and non-

serious, and deaths that occur during this period will be recorded in the source documents. All SAEs should be monitored until they are resolved or are clearly determined to be due to a subject's stable or chronic condition or intercurrent illness(es). Related AEs will be followed until resolution to baseline or grade 1 or stabilization.

8.4.1 SAE Reporting Requirements

- Participating investigators (all sites) must report all serious adverse events to the Lead Site Principal Investigator (e.g. Sponsor-Investigator) within **24 hours** of discovery or notification of the event. The participating investigator must also provide follow-up information on the SAE until final resolution.
- The Lead Site Principal Investigator will review the SAE and report the event to the FDA, external collaborator(s), and IRB as applicable.
- The Principal Investigator must send all SAEs (initial and follow-up) that require collection and reporting per protocol, and which occur in a subject who received CPX-351 as study drug, to Jazz Pharmaceuticals within 1 business day of their awareness of the SAE to [contact].
- It is the Sponsor-Investigator's responsibility (e.g. lead site PI) to ensure that ALL serious adverse events that occur on the study (e.g. ALL SAEs that occur at each enrolling institution) are reported to all participating sites.

Institutional Review Board Reporting Requirements:

- Investigative sites will report adverse events to their respective IRB according to the local IRB's policies and procedures in reporting adverse events.

8.5 SAEs and OnCore

- All SAEs will be entered into OnCore.
- A copy of the SAE form(s) submitted to the sponsor-investigator is also uploaded into Oncore.

8.6 Data Safety and Toxicity Committee

It is the responsibility of each site PI to ensure that ALL SAEs occurring on this trial (internal or external) are reported to the Case Comprehensive Cancer Center's Data

and Safety Toxicity Committee. This submission is simultaneous with their submission to the sponsor and/or other regulatory bodies.

The sponsor-investigator is responsible for submitting an annual report to the DSTC as per CCCC Data and Safety Monitoring Plan.

8.7 Data and Safety Monitoring Plan (DSMP)

This protocol will adhere to the policies of the Case Comprehensive Cancer Center Data and Safety Monitoring Plan in accordance with NCI guidelines.

9.0 PHARMACEUTICAL INFORMATION

A list of the adverse events and potential risks associated with the investigational or commercial agents administered in this study can be found in Section 8.

9.1 Investigational Agents

9.1.1 Name of Agent CPX-351

Other Names: CPX-351

Product description: CPX-351 (daunorubicin and cytarabine) liposome for injection is a combination of daunorubicin and cytarabine in a 1:5 molar ratio encapsulated in liposomes for intravenous administration. The liposome membrane is composed of distearoylphosphatidylcholine (DSPC), distearoylphosphatidylglycerol (DSPG), and cholesterol in a 7:2:1 molar ratio.

Solution preparation: The appropriate number of vials of CPX-351 (cytarabine:daunorubicin) Liposome Injection should be removed from the refrigerator prior to reconstitution. Reconstitute with 19 mL of sterile water for injection using a 20 mL syringe. Do not heat CPX-351 (cytarabine:daunorubicin) Liposome Injection. After reconstitution, invert vials gently 3- 4 times and let rest for 15 minutes and repeat vial inversion prior to withdrawing drug for dilution. The concentration of the reconstituted dispersion is 5 mg-2.2mg/mL (cytarabine-daunorubicin). CPX-351 should be diluted in approximately 500 mL of sodium chloride injection or dextrose injection.

The IV bags and infusion sets must be non-DEHP. Aseptic technique must be strictly observed throughout the handling of CPX-351 (cytarabine:daunorubicin) Liposome

Injection since no bacteriostatic agent or preservative is present. The infusion of CPX-351 (cytarabine:daunorubicin) Liposome Injection must be started within 4 hours of dilution. Vials are for single use. Unused material should be recorded as such and discarded according to institutional policies. Procedures for proper handling and disposal of anticancer drugs should be implemented.

Storage requirements: Store un-reconstituted CPX-351 vials in a refrigerator at 2°C to 8°C (36°F to 46°F) in an upright position. The vial should be stored in its original carton to protect from light.

Stability: If the diluted infusion solution is not used immediately, store in refrigerator at 2°C to 8°C for up to 4 hours.

Route of administration: The infusion of CPX-351 (cytarabine:daunorubicin) Liposome Injection will be performed through a central venous catheter, using an infusion pump to ensure that the drug is infused over the specified time period. Non-DEHP containing administration sets should be used. **Do not use an in-line filter.** CPX-351 should never be given by the intramuscular or subcutaneous route. Administer CPX-351 over approximately 90 minutes via an infusion pump. Flush the line to ensure administration of the full dose. The dosage (total mg/m²), start/stop time of the infusion, total volume infused, must be documented in the patient's chart.

Drug Procurement: CPX-351 will be supplied for this study by Jazz Pharmaceutical.

Drug Accountability: The study pharmacist or designee must maintain records of the delivery of CPX-351 to the study site, the inventory at the site, the use by each patient, and the disposition of unused product. These records should include dates, quantities, lot numbers, expiration dates and patient identifications. Institutions should maintain records that document adequately that the patients were provided the doses specified by the protocol and reconcile all investigational product received from the Sponsor. Records of storage conditions (temperature logs) must be kept for the entire period that CPX-351 is maintained at the institution.

Drug Destruction: At the completion of the study, there will be a final reconciliation of drug shipped, drug consumed, and drug remaining. This reconciliation will be logged on CASE 2918

Protocol Version 5.0

18 January 2021

the drug reconciliation form, signed and dated. Any discrepancies noted will be investigated, resolved, and documented prior to return or destruction of unused study drug. Drug destroyed on site will be documented in the study files.

10.0 EXPLORATORY or CORRELATIVE STUDIES

Bio specimens (whole blood, 10 mL) will be collected as outlined in section 11.2 at screening, C1D35 (+/- 10 days) and EOT for general research purposes, potentially including genetic analysis research. All subjects must consent to provide archived sample for future research.

All samples obtained will be stored at the Cleveland Clinic Translational Hematology and Oncology Research laboratory. Samples will remain at the Cleveland Clinic to be used for research purposes for this study as well as for future research projects approved by the IRB.

10.1 Collection of Samples

10mL of whole blood will be collected in an extra lab tube at screening, C1D35 (+/- 10 days) and EOT (section 11.2). Details and instructions about the collection, processing and shipping can be found in the Lab Manual. All samples will be housed at and should be delivered and/or shipped to:

Principle Research Technologists
Translational Hematology and Oncology Laboratory
Cleveland Clinic, [name]
[name]
[name]
[contact]

11.0 STUDY PARAMETERS AND CALENDAR

11.1 Study Parameters

11.1.1 Screening Evaluations (Consent to D-1)

1. History and physical examination.
2. ECOG performance status (Appendix I).

3. Vitals.
4. Hematology exam (Appendix IV).
5. Serum chemistry exam (Appendix IV).
6. Echocardiogram and electrocardiogram (If completed prior to consent and within 28 days of C1D1, may count towards screening procedures).
7. Bone marrow aspirate and biopsy, including cytogenetics, within 28 days of therapy start to confirm diagnosis (If completed prior to consent and within 28 days of C1D1, may count towards screening procedures).
8. Serum pregnancy test for women of childbearing potential within Child bearing potential is defined as not post-menopausal for 12 months or no previous surgical sterilization.
9. Documentation in the medical record (consisting of start date, dose, frequency, route, and if applicable stop date) of all medications including vitamins and other over the counter medications.
10. Documentation in the medical record (consisting of start and stop date, dose, frequency and route) of any prior administration of cancer agent therapy.
11. Documentation in the medical record of all adverse events (graded per CTCAE V. 5.0) present at baseline. Documentation must include start and stop dates (if resolved), relationship to CPX-351 and grade.

11.1.2 Induction Therapy (C1D1 to C1D35 and/or count recovery).

1. Physical examination will occur daily while inpatient (Appendix IV).
2. ECOG performance status will be collected daily while in-patient (Appendix I).
3. Vitals will be collected daily while in-patient (Appendix IV).
4. Echocardiogram will be completed on day 1 prior to dosing.
5. Hematology exam on days 1-5, and twice weekly during days 6-27 (Appendix IV).
6. Serum chemistry exam on days 1-5, and twice weekly days 6-27 (Appendix IV).
7. Administration of CPX-351 at 44mg/m² on days 1, 3 and 5.
8. Bone marrow aspirate and biopsy, including cytogenetics, on D35 (+/- 10 days)

9. Disease response assessment will be assessed by the treating physician on D35 (+/- 10 days) (Table 2).
10. Serum pregnancy test on C1D1 only for women of childbearing potential. Child bearing potential is defined as not post-menopausal for 12 months or no previous surgical sterilization.
11. Documentation in the medical record (consisting of start date, dose, frequency, route, and if applicable stop date) of all medications including vitamins and other over the counter medications.
12. Documentation in the medical record (consisting of start and stop date, dose, frequency and route) of any prior administration of cancer agent therapy.
13. Documentation in the medical record of all adverse events (graded per CTCAE V. 5.0). Documentation must include start and stop dates (if resolved), relationship to CPX-351 and grade.

Consolidation Therapy (C2D1 to C5D28)

1. Physical examination on day 1 of each 28 day cycle (Appendix IV).
2. ECOG performance status will be collected on day 1 of each 28 day cycle (Appendix I).
3. Vitals will be collected prior to dosing on days 1 and 3 (Appendix IV).
4. Echocardiogram will be completed prior to dosing on day 1 of every cycle
5. Hematology exam on dosing days 1 and 3 of and twice weekly during each 28 day cycle (Appendix IV).
6. Serum chemistry exam on dosing days 1 and 3 and twice weekly during each 28 day cycle (Appendix IV).
7. Administration of CPX-351 at 15.4mg/m² (daunorubicin 15.4 mg/m² and cytarabine 35 mg/m²) on days 1 and 3 of every 28 day cycle
8. Serum pregnancy test will be collected on day 1 of every 28 day cycle, only for women of childbearing potential. Child bearing potential is defined as not post-menopausal for 12 months or no previous surgical sterilization.

9. Documentation in the medical record (consisting of start date, dose, frequency, route, and if applicable stop date) of all medications including vitamins and other over the counter medications will be collected on day one of every 28 day cycle.
10. Documentation in the medical record (consisting of start and stop date, dose, frequency and route) of any prior administration of cancer agent therapy will be collected on day one of every 28 day cycle.
11. Documentation in the medical record of all adverse events (graded per CTCAE V. 5.0). Documentation must include start and stop dates (if resolved), relationship to CPX-351 and grade will be collected on day one of every 28 day cycle.

End of Treatment (EOT)

1. Physical examination (Appendix IV).
2. ECOG performance status (Appendix I).
3. Vitals (Appendix IV).
4. Hematology exam (Appendix IV).
5. Serum chemistry exam (Appendix IV).
6. Bone marrow aspirate and biopsy, including cytogenetics.
7. Disease assessment (Table 2).
8. Documentation in the medical record (consisting of start date, dose, frequency, route, and if applicable stop date) of all medications including vitamins and other over the counter medications will be collected.
9. Documentation in the medical record (consisting of start and stop date, dose, frequency and route) of any prior administration of cancer agent therapy will be collected.
10. Documentation in the medical record of all adverse events (graded per CTCAE V. 5.0). Documentation must include start and stop dates (if resolved), relationship to CPX-351 and grade will be collected.

11.2 Calendar

Period	Screening Period	Induction Phase							Consolidation Phase				End of Treatment (EOT)	Follow-up ^g
		1 cycle							Up to 4 cycles					
Day	28 Days	1	2	3	4	5	6-27	35 ^l	1 ^{dij}	2	3	4 - 28		
CPX-351 Administration ^a		X		X		X			X		X			
Informed Consent Form (ICF)		X												
Disease history and prior therapies		X												
History and physical exam ^b		X							X				X	
Vital signs ^b		X	X ^{op}		X ^{op}				X	X ^{op}		X ^{op}		
Concomitant medications		X	X							X			X	
ECOG performance status ^c		X								X			X	
Hematology ^b		X	X	X	X	X	X	X ⁿ	X	X ^e		X ⁿ	X	X ^g
Serum chemistry ^b		X	X	X	X	X	X	X ⁿ	X	X ^e		X ⁿ	X	
Pregnancy test		X	X ^k							X ^k				
Echocardiogram		X ^r	X ^q							X				
Electrocardiogram		X ^r												
Bone marrow biopsy and aspiration ^b		X ^r							X				X	
Disease response assessment ^f		X							X				X	
Correlative analysis blood draw ^m		X							X				X	
Survival follow-up														X ^h
Adverse event assessment									← X →					

- a: During the induction phase all patients will receive 44mg/m². Following the induction phase if patients achieve a response (per section 12.0) they may continue onto the consolidation phase. During the consolidation phase patients will receive 15.4mg/m² (daunorubicin 15.4 mg/m² and cytarabine 35 mg/m²) for up to 4 cycles.
- b: See Appendix IV for required tests.
- c: See Appendix I for performance status grading.
- d: Indicates at +/-3 day window.
- e: Required twice weekly to monitor counts, can be completed at a local laboratory.
- f: See Section 12.0 for MDS response assessment criteria.
- g: Follow up will occur monthly as SOC for the first 6 months of follow-up. See section 6.4 for adverse event reporting requirements.
- h: Survival Follow up will occur bimonthly (60 days) for a duration of 1 year from patient's EOT visit.
- i: During only the first cycle in consolidation phase, CPX-351 must be given no earlier than 35 days after the start of induction and no later than 75 days after the start of induction. There should be 35 days between the start of each subsequent consolidation cycles. Patients must have recovered to ANC >500/ μ L and platelets >50,000/ μ L to be eligible for any consolidation therapy.
- j: Prior to the first cycle of consolidation therapy, patient must have an ECOG PS of 0-2.
- k: Must be negative prior to dosing.
- l: Indicates a +/-10 day window.
- m: 10mL of whole blood will be collected in an extra lab tube for these tests.
- n: Hematology and serum chemistry will be assessed 1-3x weekly at the discretion of the treating physician to monitor counts. These can be completed at a local laboratory.
- o: On dosing days, for induction phase only, vitals must be collected prior to infusion, 5, 10, 30 and 60 minutes post the start of infusion and at the end of infusion. On dosing days, for consolidation phase, vitals must be collected prior to infusion and at the end of infusion.
- p: Indicates a (+/-) 5 minute window.
- q: Required if patient has not had an ECHO within 28 days of C1D1.
- r: If completed prior to consent and within 28 days of C1D1, may count towards screening procedures.

12.0 MEASUREMENT OF EFFECT

Response criteria will be defined by the IWG criteria ET 2006. Patients will be assessed for response at the end of induction cycle.

Response criteria will be defined as follow:

Response	Definition Responses must be for at least 4 weeks)
Complete remission (CR)	Marrow: < 5% myeloblasts with normal maturation of all cell lines. Persistent dysplasia will be noted (dysplastic changes should consider the normal range of dysplastic changes.) Blood: 
- Hemoglobin (Hgb) \geq 11 g/dL (untransfused, patient not on EPO)- Neutrophils \geq 1x10⁹/L (not on myeloid growth factor)- Platelets \geq 100 x 10⁹/L (not on thrombopoietic agent)- No blasts
Partial remission (PR)	All CR criteria (if abnormal prior to treatment), except: Marrow blasts decreased by \geq 50% compared with pretreatment but still $>$ 5%. Cellularity and morphology not relevant
Marrow CR	Marrow: \leq 5% myeloblasts and decrease by \geq 50% over pretreatment Blood: if hematologic improvement (HI) responses, they will be noted in addition to the marrow CR
Stable disease (SD)	Failure to achieve at least PR, but no evidence of progression for $>$ 8 weeks
Failure	Death during treatment or disease progression characterized by worsening of cytopenias, increase in percentage of marrow blasts, or progression to an MDS FAB subtype more advanced than pretreatment.

Relapse after CR or PR (PD)	
At least one of the following:
 
 - Return to pretreatment bone marrow blast percentage - Decrement of $\geq 50\%$ from maximum remission/response levels in granulocytes or platelets - Reduction in Hgb concentration by ≥ 1.5 g/dL or transfusion dependence (in the absence of another explanation, such as acute infection, GI bleeding, hemolysis, etc.)
Cytogenetic response	
Complete: Disappearance of the chromosomal abnormality without appearance of new ones
 
Partial: At least 50% reduction of the chromosomal abnormality

Hematologic Improvement	Response Criteria (responses must last at least 8 weeks)
Erythroid response (pretreatment, < 11 g/dL)	
Hgb increase by ≥ 1 g/dL
 
Relevant reduction of units of RBC transfusions by an absolute number of at least 4 RBC transfusions/8wk compared with the pretreatment transfusion number in the previous 8 wk.
 
Only RBC transfusions given for a Hgb of ≤ 9 g/dL pretreatment will count in the RBC transfusion response evaluation

Platelet response (pretreatment, $< 100 \times 10^9/L$)	
Absolute increase of $\geq 30 \times 10^9/L$ for patients starting with $> 20 \times 10^9/L$
 
Increase from $< 20 \times 10^9/L$ to $> 20 \times 10^9/L$ and by at least 100%

Neutrophil response (pretreatment, $< 1 \times 10^9/L$)	
At least 100% increase an absolute increase $> 0.5 \times 10^9/L$

Progression or relapse after HI	
At least 1 of the following:
 
At least 50% decrement from maximum response levels in granulocyte or platelets
 
Reduction in Hgb by ≥ 1.5 g/dL
 
Transfusion dependence (in the absence of another explanation, such as acute infection, GI bleeding, hemolysis, etc.)

Table 3: Response Criteria for MDS Patients

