2.0 Study Objectives

2.1 Primary Objective

- Evaluate the efficacy of CPX-351 as measured by overall response rate (ORR), i.e. by IWG 2006 criteria for MDS patients after Hypomethylating agent failure.

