The consolidation phase is defined as C2D1 to C5D28 or once the patients meet EOT criteria (section 6.3, Table 1). Only patients with a documented response (CR, CRI, or PR) from the D35 (+/-10 days) bone marrow are eligible for consolidation therapy. Prior to the first cycle of consolidation therapy the patients must have a PS of 0-2. During the consolidation phase, CPX-351 must be given no earlier than 35 days after the start of induction and no later than 75 days after the start of induction. For all subsequent cycles, there must be at least 35 days between the start of each cycle. Patients must have recovered to ANC >500/ µL and platelets >50,000/µL to be eligible for any consolidation therapy.

During the consolidation phase, CPX-351 will be given at 15.4 mg/m² (daunorubicin 15.4 mg/m² and cytarabine 35 mg/m²) on days 1 and 3 of each 28 day cycle. Consolidation therapy can be continued up to 4 cycles in the absences of toxicities or reasons that require discontinuation and/or any EOT criteria (section 6.3, Table 1).

Premedication with anti-emetics is recommended prior to treatment with CPX-351. No other chemotherapy consolidation treatment is permitted. Only HSCT (hematopoietic stem cell transplant) is permitted in place of, or following, chemotherapy consolidation. Delays in administrating consolidation cycles will be allowed at the discretion of the treating physician and after discussion with the PI.

End of Treatment and Follow-up

At the point in which the patient completes therapy per protocol or meets any EOT criteria (section 6.3, Table 1), the patient will enter into the follow-up period. The patient will be followed for survival for 1 year and/or until death, whichever occurs first. During the first 6 months of follow-up the patient will be seen in clinic as standard of care (SOC) every 30 days, per the study calendar (section 11.2). End of study (EOS) is defined as the time the patient completes 1 year of follow, withdraws consent and/or patient's death, whichever occurs first.

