14.0 STATISTICAL CONSIDERATIONS

In determining the sample size for the patient cohort, Minimax Simon's two-stage design (Simon, 1989) will be used. The null hypothesis that the true response rate is 0.1 will be tested against a one sided alternative. In the first stage, 7 patients will be accrued in each arm. If there are two or less responses in these 7 patients, the arm will be stopped. Interim analysis will be conducted to determine the benefit of applying the drug in each arm. In the winning arm, 11 additional patients will be accrued for a total of 18. The null hypothesis will be rejected if 4 or more responses are observed in 18 patients. This design yields a type I error rate of 0.1 and power of 0.8 when the true response rate is 0.3.

Descriptive statistical analysis will be calculated, including histograms or box-plots, proportions, range, means and standard deviations. Fisher's exact test and Wilcoxon rank test will be used in univariate analyses of categorical and continuous variables, respectively. Overall response (CR + CRI +) rate and its 95% CI. Given there is no adjustment for multiple comparisons, need to note the p-values from the univariate analyses will be nominal and not used to infer significance.

Toxicity Monitoring Rules

The following toxicity monitoring plan will terminate the trial early given evidence for excessive rates of toxicity with CPX-351 based on the method of Thall et al.¹⁴ Early termination will be applied to evaluate patients experiencing toxicity defined as any grade ≥ 3 non-hematologic AE that is determined to be at least possibly related to CPX-351. A total of 25 patients will be enrolled. The monitoring rules target a toxicity rate of 20% and assume a non-informative Beta (0.2, 0.8) prior distribution. The trial will stop early for toxicity if $\text{Pr}(\text{Toxicity Rate} > 0.20 | \text{data}) > 0.85$, i.e. stop early if the evidence for excessive toxicity (higher than 20%) for the target population given observed data is sufficiently high (probability > 0.85). Monitoring will be carried out

from the 3rd patient. Table 5 summarizes the resultant stopping boundaries and Table 6 summarizes the trial's operating characteristics.

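### The response table leaves exactly 5% marrow blasts in neither CR nor PR, and the plan does not say whether the remaining category, Marrow CR, counts in the primary response rate

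*Combined protocol and SAP*

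**What the plan says.** Section 2.1 makes ORR the measure of efficacy and defers to IWG 2006 for its definition. It does not list the categories that make up the ORR. Section 14.0 gives a list, but as read it breaks off: "Overall response (CR + CRI +) rate and its 95% CI".

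The response table in section 12.0 (Table 3) sets the marrow limits:

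- CR: "Marrow: < 5% myeloblasts with normal maturation of all cell lines", with hemoglobin, neutrophil and platelet minima and no blood blasts.
- PR: the CR criteria, except that blasts have fallen by at least 50% "compared with pretreatment but still" above 5%.
- Marrow CR: 5% or below, with a fall of at least 50%. No blood-count minimum is set.
- Stable disease: "Failure to achieve at least PR, but no evidence of progression for" more than 8 weeks.

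CRi has no row. Sections 3.1 and 6.1 use CR, CRi and PR as the condition for further treatment; section 6.1 reads "Only patients with a documented response (CR, CRI, or PR) from the D35 (+/-10 days) bone marrow are eligible for consolidation therapy".

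**The concern.** The CR row excludes 5% from below and the PR row excludes it from above, so one attainable blast value has no place on the CR/PR scale even when the blood counts have fully recovered. If only CR, CRi and PR count as responses, the primary endpoint is non-monotone at its own cut-point: a reading of 4% counts, 5% does not, and 6% can count again.

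Two things depend on this classification. The first is the test, which rests on very few events: 4 or more responses in 18, after a first stage of 7 per arm. The second is entry to consolidation, which uses the same category names.

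**Working it through.** **Step 1. Classify a patient with full count recovery at and around 5%.**

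A fall of at least 50% to 5% needs a baseline of at least 5/0.5 = 10%. A fall of at least 50% to 6% needs at least 6/0.5 = 12%.

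| Baseline | Day 35 | CR (<5%) | PR (fall ≥50%, >5%) | Marrow CR (≤5%, fall ≥50%) |
|---|---|---|---|---|
| 14% | 4% | yes | no | yes |
| 14% | 5% | no | no | yes (fall 9/14 = 64%) |
| 14% | 6% | no | yes (fall 8/14 = 57%) | no |
| 9% | 5% | no | no | no (fall 4/9 = 44%) |

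From a 14% baseline, the 5% patient is a Marrow CR and nothing higher. From a 9% baseline, only stable disease or hematologic improvement remains. Both need 8 weeks of observation, which the day 35 marrow cannot supply.

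**Step 2. Ask whether the 5% patient counts in ORR.**

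- Section 2.1 defers to IWG 2006 and lists nothing.
- Section 14.0 names CR and CRi; the term after the second plus sign is missing as read.
- Sections 3.1 and 6.1 list CR, CRi and PR, but as the condition for consolidation.
- No section says that Marrow CR or hematologic improvement counts.

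If ORR = CR + CRi + PR, the 5% patient is a non-responder. CRi does not help on its plain meaning, because counts have recovered. The 6% patient in the table is a responder. If Marrow CR counts, the 14%-to-5% patient is a responder and the reversal disappears. The 9%-to-5% patient would still have to count through hematologic improvement, if that is included.

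**Step 3. Reproduce the design figure.**

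Inputs from section 14.0: p0 = 0.10, p1 = 0.30, 7 then 18 patients, reject at 4 or more, stated type I error 0.1 and power 0.8.

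P(reject) = sum over x1 > r1 of Bin(x1; 7, p) × P(Bin(11, p) ≥ 4 − x1)

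| Stage 1 stop | Type I error at 0.10 | Power at 0.30 |
|---|---|---|
| r1 = 0 (stop at 0/7) | 0.0893 | 0.800 |
| r1 = 2 (as written, stop at 2 or fewer) | 0.0185 | 0.348 |

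The stated power is reproduced only with stopping at 0/7. The mismatch with the written stage 1 rule is a separate issue and neither supports nor weakens this point. The stop-at-0 rule is used below because it matches the stated power.

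**Step 4. Illustrate the cost.**

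Assumption: a share f of true responders reads exactly 5% with full counts and is lost, so the effective rate is 0.30 × (1 − f). The documents give no value for f.

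| f | Effective rate | Power (stop at 0/7, reject at 4/18) |
|---|---|---|
| 0 | 0.300 | 0.800 |
| 2% | 0.294 | 0.786 |
| 5% | 0.285 | 0.762 |
| 6% | 0.282 | 0.754 |

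**Step 5. How often one patient decides.**

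3/18 = 16.7% does not reject; 4/18 = 22.2% does. One patient is 1/18 = 5.6 percentage points. At a true rate of 0.30, the probability of continuing and ending on exactly 4/18 is 15.0% with stopping at 0/7, and 2.3% under the written stage 1 rule. Under the written rule the sensitive point moves to stage 1: Bin(3; 7, 0.30) = 35 × 0.3³ × 0.7⁴ = 22.7% of arms have exactly 3/7, where losing one responder stops the arm. Section 6.1 also uses stage 1 responses to choose the arm that continues.

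**The case against.** The strongest reply is that exactly 5% is not unclassified. The Marrow CR row takes it whenever blasts halved, and nothing excludes Marrow CR from ORR. The missing term in section 14.0 may be a loss in text reading. Since CRi has no row, Marrow CR may have been meant to serve as CRi. If ORR were only CR + CRi in the ordinary sense, neither the 5% nor the 6% patient would count, and there would be no reversal. This stands: a reader might infer that the 5% patient certainly drops out of the primary ORR, and the documents do not establish that. Exclusion is an inference from the consolidation lists.

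A reader might also infer from the growth-factor wording in sections 6.1 and 6.2, which turns on blasts above 5%, that the rest of the protocol treats 5% as cleared. That wording is a treatment permission, not a response boundary. Only the Marrow CR row is direct evidence.

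The effect is also easy to overstate. The loss requires 5% blasts and full count recovery in the same patient, so the chance that any of 18 marrows reads 5% is not the chance of harm. The unadjusted chance of exactly 4 responders in 18, 16.8% at a rate of 0.30, ignores stage 1.

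Finally, the CR sign could itself be a misread character. That is possible, but the at-most sign is read correctly in the Marrow CR row of the same table.

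None of this closes the gap between the CR and PR rows, nor does it help a patient whose baseline was below 10%.

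**Conclusion.** The point holds as a narrow defect in an endpoint definition. As written, exactly 5% blasts with full count recovery is neither CR nor PR; it is Marrow CR from a baseline of 10% or more, and at most stable disease or hematologic improvement from a lower one. Whether this removes the patient from the primary ORR depends on a list the plan leaves incomplete. On the best-supported reading, CR + CRi + PR, it does, and the endpoint is then non-monotone at 5%.

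The likely effect on power is small: 1.4 to 4.6 percentage points (0.800 − 0.786 to 0.800 − 0.754), if 2% to 6% of true responders are affected. That range is assumed, not taken from the documents. The point still deserves correction because one patient can decide either stage and the remedy needs no new data. The consolidation consequence does not depend on the ORR list: on the plain meaning of CRi, a patient with full counts at 5% falls outside all three categories named in sections 3.1 and 6.1.

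**What to change.** 1. In the section 12.0 response table, make the CR and PR rows meet at 5%. Writing the CR limit as ≤ 5% does this and matches the Marrow CR row. Confirm the wording against the IWG 2006 criteria that the protocol cites before adopting it, since they are the stated standard.
2. In section 14.0, complete the list of ORR components and say explicitly whether Marrow CR counts.
3. Reconcile sections 3.1, 6.1 and 12.0. The same categories decide entry to consolidation, so a change to the CR row also changes who meets that condition. No clinical rule is proposed here; the investigators should settle it knowingly.

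Cost: a one-character change to the CR row plus a completed list, with no new data and no change to the sample size of 7, 18 or 25. The downside is that any marrow already reported at exactly 5% must be reclassified.
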